8.0 Sharing of Results with Subjects*

Participant providers are part of the Adolescent treatment network (ATN) and may access the findings of the study once published through this network.

9.0 Study Timelines*

At this time all participants are enrolled and all sites have either begun or completed the implementation phase. All sites are projected to complete participation by November 2020.

PROTOCOL TITLE: TMI

10.0 Subject Population*

The table below provides a breakdown of the current participant pool and participation in the beginning of cycle 8. Participants are affiliated with clinical sites within the ATN.

PROGRESS BY SITE		
Site 1		
17	Total Consented	
6	Discontinued TMI participation	
11	Active (current participants)	
0	Completed this cycle	
11	Not completed	
Site 2		
19	Total Consented	
6	Discontinued TMI participation	
13	Active (current participants)	
2	Completed this cycle	
11	Not completed	
Site 3		
18	Total Consented	
8	Discontinued TMI participation	
10	Active (current participants)	
0	Completed this cycle	
10	Not completed	
Site 6		
29	Total Consented	
9	Discontinued TMI participation	
20	Active (current participants)	
3	Completed this cycle	
17	Not completed	
Site 7		
18	Total Consented	
3	Discontinued TMI participation	
15	Active (current participants)	
1	Completed this cycle	
14	Not completed	
Site 8		
16	Total Consented	
4	Discontinued TMI participation	
12	Active (current participants)	
0	Completed this cycle	
12	Not completed	
Site 10		
11	Total Consented	
1	Discontinued TMI participation	
10	Active (current participants)	
0	Completed this cycle	
10	Not completed	
Site 11		
15	Total Consented	
4	Discontinued TMI participation	
11	Active (current participants)	
0	Completed this cycle	
11	Not completed	
Site 12		
24	Total Consented	
5	Discontinued TMI participation	
19	Active (current participants)	

PROTOCOL TITLE: TMI

0	Completed this cycle
0	Not completed
Site 13	
23	Total Consented
5	Discontinued TMI participation
18	Active (current participants)
2	Completed this cycle
16	Not completed
TOTAL	
190	Total Consented
51	Discontinued TMI Participation
139	Active (current participants)
8	Completed this cycle
112	Not completed this cycle

11.0 Vulnerable Populations*

N/A

12.0 Local Number of Subjects

N/A – all participants are at external sites.

13.0 Recruitment Methods

N/A – the study is no longer recruiting participants. Participants were recruited using the following protocol: “The site Co-PI or his/her designated research staff will complete the TMI Potential Participants form (attached) to refer potential staff to the TMI research staff for potential participation in TMI. The site Co-PI's and site designated research staff will have to option to provide referred staff at their site with an initial introduction to TMI. This introduction will include a review of the TMI information sheet, along with a description the basic procedure and time commitment for the training and implementation of the study. Staff will be informed that participation is voluntary and they will be provided with an opportunity to ask questions. TMI research staff will be available to attend the introductory meeting by telephone or Skype if the site Co-PI so desires. Alternatively, TMI research staff will conduct the introductory meeting by telephone or Skype with referred staff as a group or individually. Referred staff will be encouraged to follow up with TMI research staff individually with additional questions or to decline participation. Referred staff may also decline participation at any time through their site Co-PI or designated representative if they so desire. Once the Co-PI or designated representative has confirmed that the referred staff have received an initial introduction to the TMI study, TMI research staff will contact each referred staff member by email to invite them to participate in TMI by completing a TMI role play. The procedures for scheduling a role play will be described and staff will be reminded that their completion of a TMI role play is their consent to participate in the study (this is described in the information sheet as well). The information sheet will be included in this recruitment contact and staff will be encouraged to review it if they have not already done so and to contact the TMI research staff by phone or email with questions or concerns (recruitment email content is included in the Email Templates document). Interested staff members will initiate scheduling an appointment for a TMI role play. At the time of the TMI role play appointment, the study staff member conducting the role play will verbally confirm with the staff member that s/he understands that completion of the role play is his/her consent to participate in the TMI study. If the staff member confirms, then the TMI role play is completed. If the staff member does not confirm, or has additional questions, the actor will

PROTOCOL TITLE: TMI

refer him/her to the TMI project coordinator or TMI senior project assistant for follow-up. The staff member can choose to complete the role play at that time (enrolling in the TMI study), delay a completion decision until after s/he has contacted the TMI project coordinator or senior project assistant, or decline participation in TMI.”

14.0 Withdrawal of Subjects*

Participants may choose to leave the study at any point. Participants may be removed from the study based on changes in their clinical role and if they have less than 4 hours of client contact per week on average. Participant data will be included, unless a participant requests that their data is removed. In such cases, the participant’s data will be deleted.

15.0 Risks to Subjects*

This study carries no known risks to participants, because it is a study of motivational interviewing (MI) training for staff and implementation of MI in HIV ATN network clinical sites.

16.0 Potential Benefits to Subjects*

Participants will hone new skills expected to be beneficial to increasing the adherence of the youth they serve in their HIV clinics. Motivational interviewing (MI) is a set of skills to expand the capacity of people working with youth living with HIV to provide culturally competent care services and increase successful care outcomes. Participants in this study will receive intensive training and support in MI to improve communication with youth living with HIV during HIV care visits, to improve outreach, as well as prevention programs.

17.0 Data Management* and Confidentiality

Data will be analyzed using formative, longitudinal, qualitative, and quantitative methods. Participants are identified in the research records only by a codename or number. Site staff do not have access to individual participant competency scores, but the iTeam is aware of the extent of participation and aggregated competency. Percentages of site participants above or below competency are shared with the iTeam only after the end of each cycle to avoid inadvertently compromising participant privacy. All staff involved on the project have completed the necessary CITI human subjects training.

In regard to data management, the TMI coding lab functions as a forum to train coders in use of the Motivational Interviewing Coach Rating Scale (MI-CRS), to improve the utility of the MI-CRS, and to coordinate and monitor the ongoing inter-rater reliability (IRR) of coders. Coders use recorded roleplays as practice for coding to maintain the reliability of the data.

18.0 Provisions to Monitor the Data to Ensure the Safety of Subjects*

N/A

19.0 Provisions to Protect the Privacy Interests of Subjects

Participants are identified in the research records only by a codename or number. Site staff do not have access to individual participant competency scores, but the iTeam is

PROTOCOL TITLE: TMI

aware of the extent of participation and aggregated competency. Percentages of site participants above or below competency are shared with the iTeam only after the end of each cycle to avoid inadvertently compromising participant privacy. Participants complete some group trainings (i.e., MI workshop), but may choose to end participation or withdraw from the study at any time. Participants may choose not to answer questions that cause them discomfort. Only approved staff will have access to participant data.

20.0 Compensation for Research-Related Injury

N/A

21.0 Economic Burden to Subjects

N/A

22.0 Consent Process

A waiver of documentation of consent was previously approved for the current study; however, the TMI information sheet was provided to all participants at the time of the initial introduction to TMI or emailed to them ahead of time. It was provided by email again when the recruitment email was sent. Consent was discussed verbally immediately prior to completion of the first TMI role play. Documentation of consent was not obtained as completion of a role play is considered consent to participate.

23.0 Process to Document Consent in Writing

N/A – a waiver of documentation of consent was previously approved for this study.

24.0 Setting

This is a sub-study associated with the larger SIU study, in which we use the same sites for other associated studies. These sites are a part of the Adolescent Medicine Trials Network for HIV/AIDS Intervention (ATN); please reference protocol number 2017.21748. Research has been ongoing at these sites since 2017.

25.0 Resources Available

Participants have already been recruited and are involved in ongoing research at the sites listed above and below. The CTBScience and FSU College of Medicine are providing other resources not described in site reliance agreements. Multiple study personnel are clinical psychologists and health professionals in the case of an unexpected adverse event.

26.0 Multi-Site Research* (Delete this section if this is not a Multi-Site Research Study.)

Below, presented in the table, are the number of participants active in the study by clinical site for the beginning of cycle 8. All recruitment is complete at this phase of the study. All sites have

PROTOCOL TITLE: TMI

existing reliance agreements with the FSU IRB. See attached for the communications worksheet between sites. Communication is open and ongoing between the study team, Site co-PIs, and Study Coordinators. Our team has a designated communication liaison who completes a majority of communication between the team and sites in order to reduce possible confusion.

PROGRESS BY SITE	
Site 1	
17	Total Consented
6	Discontinued TMI participation
11	Active (current participants)
0	Completed this cycle
11	Not completed
Site 2	
19	Total Consented
6	Discontinued TMI participation
13	Active (current participants)
2	Completed this cycle
11	Not completed
Site 3	
18	Total Consented
8	Discontinued TMI participation
10	Active (current participants)
0	Completed this cycle
10	Not completed
Site 6	
29	Total Consented
9	Discontinued TMI participation
20	Active (current participants)
3	Completed this cycle
17	Not completed
Site 7	
18	Total Consented
3	Discontinued TMI participation
15	Active (current participants)
1	Completed this cycle
14	Not completed
Site 8	
16	Total Consented
4	Discontinued TMI participation
12	Active (current participants)
0	Completed this cycle
12	Not completed
Site 10	
11	Total Consented
1	Discontinued TMI participation
10	Active (current participants)
0	Completed this cycle
10	Not completed
Site 11	
15	Total Consented
4	Discontinued TMI participation
11	Active (current participants)
0	Completed this cycle
11	Not completed
Site 12	
24	Total Consented
5	Discontinued TMI participation

PROTOCOL TITLE: TMI

19	Active (current participants)
0	Completed this cycle
0	Not completed
Site 13	
23	Total Consented
5	Discontinued TMI participation
18	Active (current participants)
2	Completed this cycle
16	Not completed
TOTAL	
190	Total Consented
51	Discontinued TMI Participation
139	Active (current participants)
8	Completed this cycle
112	Not completed this cycle

1. LIST OF ABBREVIATIONS

AC	(SIU) Analytic Core
ART	Antiretroviral Treatment
ATN	Adolescent Medicine Trials Network for HIV/AIDS Interventions
CoP	Community of Practice
CT	Change Talk
DAP	Dynamic Adaptation Process
DWLD	Dynamic Wait-listed Design
EBP	Evidence-Based Practice
EPIS	Exploration, Preparation, Implementation, Sustainment Model
IRT	Item Response Theory
IS	Implementation Science
ISC	(SIU) Implementation Science Core
MC	(SIU) Management Core
MI	Motivational Interviewing
MOO	Manual of Operations
MPIs	Main Principle Investigators
PI	Principle Investigator
REC	(SIU) Recruitment and Enrollment Center
SC	Site Coordinator
sIRB	Single Institutional Review Board
SIU	Scale It Up
TMI	Tailored MI Implementation Intervention
TMI Team	Coordination Team, excluding Study Sites
YLH	Youth Living with HIV

2. INTRODUCTION

2.1. Background

The goal of this study is to test a multi-faceted Tailored Motivational Interviewing Implementation Intervention (TMI) in a hybrid type-3 implementation-effectiveness trial using a dynamic wait-listed design. The TMI intervention is based on the Dynamic Adaptation Process (DAP—which aims to balance flexibility and fidelity—to scale up an Evidence-Based Practice (EBP) in multidisciplinary adolescent HIV care settings.

2.2. Objectives/Research Hypotheses

2.2.1. Primary Objective

The objective of this study is to determine the effect of TMI on provider competency.

Specific Aims:

- 1) To determine the effect of TMI on provider MI competency, and secondarily HIV care cascade outcomes, in 10 multidisciplinary adolescent HIV care teams.
- 2) To compare internal facilitation plus Communities of Practice (CoPs) to CoPs alone in sustaining fidelity.
- 3) To explore the role of the barriers and facilitators to implementation identified in the EPIS model as these impact on provider MI competency.
- 4) To determine the cost effectiveness of TMI with or without internal facilitation sustainment by combining fidelity and cascade outcomes with monies spent on implementation strategies.

Primary Hypotheses:

- 1) MI competency will increase during the TMI phase relative to the baseline phase.
- 2) During the sustainment phase, the level of MI competence from the Implementation phase will be maintained. (Exploratory)
- 3) During the sustainment phase, CoP with IF will have better maintenance of MI competence relative to CoP only. (Exploratory)
- 4) Cascade-related outcomes—including viral load detectability, number of clinic visits among YLH, number of youth tested and linked to care—will improve during the implementation and sustainment phases relative to the baseline phase.

2.2.2. Secondary Objective

2.2.3. Other Objectives

2.3. Outcomes

[To list and briefly describe the outcomes of interest]

2.3.1. Primary Outcomes

The primary Outcome is MI Competency, which includes a raw average score and a criterion score (Beginner, Novice, Intermediate, Advanced). The MI Coach Rating Scale was developed and evaluated as part of [name] NHLBI funded center grant and in our preliminary studies (NIMH R34 for TMI, ATN 128 Peacock). It was developed and evaluated using methods based in Item Response Theory (IRT), specifically, Rasch models, Many-Facet Rasch Models (MFRMs), and item bifactor measurement models.. The MI-CRS is comprised of 12 items that are rated on a 4-point ordered categorical scale (*Poor, Fair, Good, Excellent*) by trained observational coders, supervisors, or other TMI team members. The ratings are based on observation of a provider-patient interactions, whether a recording of an actual interaction or a standardized patient interaction. Psychometric performance of the MI-CRS is detailed in [name] et al. (in press).

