Organizational Supports. While many aspects of this implementation strategy are adaptable, organizational leadership will review data on completion of the role play and coaching sessions and will determine corrective action for suboptimal adherence. Each site will receive the same incentive budget (equivalent of \$50 per staff member) and will determine whether incentives will be provided episodically or after program completion. The iTeam will decide how to deliver incentives (i.e., directly to individuals for completion of program requirements, utilize a lottery system, or provide a group reward when all site participants adhere to program requirements); however, beginning in cycle 8, participants must be provided at least a \$10 incentive for completing role plays.

Sustainment. The iTeam will guide the site(s) to develop a community of practice (CoP). CoPs are based on a view of learning as an individual and social phenomenon rather than a one-way transfer of formal knowledge between groups or individuals. By having providers participate in the implementation phase, a CoP is already beginning to develop at the sites. The iTeam will guide the continued development of the CoP as needed by assisting with scheduling and setting meeting agendas to encourage MI practice, peer coaching and potentially fidelity monitoring, and prevent drift. In addition to CoP, half the sites will be randomized to receive 0.1 FTE of funding during the sustainment period for an internal facilitator who will be trained to continue quarterly fidelity monitoring and coaching feedback when scores fall below competency. The funding may be split among two facilitators to account for staff turnover. The iTeam will choose the facilitator(s) based on participant competency, provider interest and motivation, and the participant's role within the organization. The chosen internal facilitator will be given the option of declining this position for any reason. If they choose to accept the appointment, they will be asked to sign a release of information to help the study team and site ensure their ability to act in the role of internal facilitator. The internal facilitator will be able to choose how much information is shared and with whom the information will be shared.

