6.0 Procedures Involved*

Participants will be part of a multi-phase motivational interviewing (MI) implementation program through the sites where they are employed. MI training will be conducted at sites as part of ongoing professional development.

Participation in the study includes:

PROTOCOL TITLE: TMI

(1) Fidelity Assessments: Quarterly for three years, participants will complete audio recorded standardized patient interactions (a total of 13) over the phone (approximately 30 minutes each) with a study staff member. The study staff member will role play as a patient with HIV and record the session, which will be rated using the MI Coach Rating Scale. This is being done to conduct assessments of their MI skills.

(2) MI training. An MI training workshop will be conducted as part of professional development at the sites. The timing of the training will depend on randomization (two sites are randomized to receive MI training every three months for up to 15 months). Prior to a participant's site's MI training, they will complete standard patient interactions quarterly. While the total number of interactions does not change, the number of interactions they do prior to training depends on their sites randomization and will vary from 2 to a maximum of 6. In the period following initial training, but before the next fidelity assessment, participants will complete two 1-hour coaching sessions over the phone. Following this period, participants may receive additional coaching quarterly for one year following the fidelity assessments described above.

After one year, sites will be randomized to internal facilitation (a person from each site will be chosen to be an MI supervisor to be available for ongoing fidelity monitoring and coaching) plus CoP (the site will decide how to meet as a group to continue MI practice), or to CoP only.

Implementation Teams (iTeams): There will also be an opportunity for some participants to be part of the iTeam at each site. The iTeam will meet monthly to review study progress and make recommendations for how best to implement and sustain MI at each Tailored Motivational Interviewing (TMI) Implementation Intervention site.

Data is formative, longitudinal, qualitative, and quantitative in nature.

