5.2. Specification of Key Variables

5.2.1. Outcomes

	Outcome Type [e.g. primary, secondary, etc.]	Variable Name [To include Calculation/Transformation Specifications, if derived]	Definition [to include reference to definition or name of author/coauthor that provided definition. To specify timings, specific measurements, units of measurement.]	Primary/Key Secondary Endpoints [if applicable; listed in order of importance]	Algorithm for Value Calculation in Case of Partially Complete Data
MI Competency, Raw Average Score	Primary	MICRS_AV	MI Competency, Raw Average Score on the 12-Item MI Coach Rating Scale		Mean(MIRating1 to MIRating 12)

			(MI-CRS), Ranging from 1-4		
MI Competency, Criterion Score	Primary	MICRS_CR	MI Competency Level, Criterion Score (Beginner, Novice, Intermediate, Advanced), Ordered Categorical Criterion Score Based on Defined Thresholds for Competency Raw Scores		
HIV Care Cascade Related Outcomes, ***	Secondary	Viral Load			
...					

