5.2.3. Covariates

	Variable Name (or Calculation/	Definition	Additional Details

	Transformation Specifications if derived)	[to include timings, specific measurements, units of measurement].	(as needed)
Implementation Phase Indicator	PH_IMP	Dummy-Coded Indicator for Measurements in the Implementation Phase	
Sustainment Phase Indicator	PH_SUS	Dummy-Coded Indicator for Measurements in the Sustainment Phase	
Linear Time	L_MO	Linear number of months from the start of the Baseline Phase	
Linear Time, Implementation	L_MO_IM	Linear number of months from the start of the Implementation Phase	
Linear Time, Sustainment	L_MO_SU	Linear number of months from the start of the Sustainment Phase	
Sustainment Phase Condition	COND_IF	Indicator for sites randomized to the CoP with IF condition in the Sustainment Phase	

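### The primary MI-CRS score is an unadjusted item mean from more than one coder, and the primary model has no coder term; if the coder mix changed over the study, leniency differences could load on PH_IMP

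*SAP*

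**What the plan says.** SAP 2.3.1 names two versions of the primary outcome: "The primary Outcome is MI Competency, which includes a raw average score and a criterion score". SAP 5.2.1 computes the raw score as "Mean(MIRating1 to MIRating 12", an average over items. The criterion score is obtained by applying thresholds to the raw score, so it inherits whatever the raw score contains.

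On who rates, SAP 2.3.1 describes the scale as scored "by trained observational coders, supervisors, or other TMI team members". Protocol 5.0 says research assistants code the recordings used for feedback. Protocol 17.0 describes a coding lab that trains coders, in the plural, and exists in part "to coordinate and monitor the ongoing inter-rater reliability (IRR) of coders". Protocol 6.0 adds the other party to each recording: "The study staff member will role play as a patient with HIV and record the session".

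SAP 2.3.1 says the scale was developed with Item Response Theory methods, "specifically, Rasch models, Many-Facet Rasch Models (MFRMs), and item bifactor measurement models". No rater-adjusted measure is carried into the trial score.

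The covariate table (SAP 5.2.3) holds phase indicators, time terms and the sustainment condition. Its first time term, L_MO, is "Linear number of months from the start of the Baseline Phase". The primary model (5.4.1) nests measurements within providers, with cluster or site indicators, phase indicators and polynomial time. The planned search for further controls (5.3, item 2) is limited to provider variables. Coder and actor therefore have no planned way into the model.

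**The concern.** A many-facet Rasch model can carry a term for rater severity; a raw item mean cannot. Two coders who are each consistent can still differ steadily in leniency, and that difference stays in the score. Reliability monitoring reduces it but does not adjust for it.

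In a parallel-group trial with random allocation of recordings, this would mostly be noise. Here phase is tied to calendar time: early recordings are mostly baseline, and later ones are implementation or sustainment. A change in the coder group is a step in calendar time, and a straight line in months cannot absorb a step. What remains can load on PH_IMP, the coefficient that tests Hypothesis 1. The provider random intercept does not capture it, so the Wald standard error is too small. The error can run for or against TMI. It needs no unmasking and no change in how any one coder scores.

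**Working it through.** **1. The plan's own figures.** SAP 3.3.1 uses n_eff = n / [1 + (m − 1)ρ].
- Repeated measurements: 10 × 18.9 × 6.5 = 1,228.5, and 1,228.5 / [1 + 5.5 × 0.35] = 1,228.5 / 2.925 = 420. Starting from the stated 1,237 gives 422.9.
- Sites: 420 / 10 = 42 per site, and 420 / [1 + 41 × 0.09] = 420 / 4.69 = 89.6, stated as 90.

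Both figures reproduce. The calculation counts clustering by provider and by site, and none by coder.

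**2. Formula for the size.** The SAP sets p < .05 (5.1.1), taken here as two-sided. If the model reports SE_model and the true sampling error is SE_true, the false-positive rate is 2 × P(Z > 1.96 × SE_model / SE_true). A true SE 10% larger than reported gives 2 × P(Z > 1.78) = 7.5%; 20% larger gives 2 × P(Z > 1.63) = 10.2%.

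**3. Inputs.**
- From the SAP: 10 sites in five clusters, about 19 providers per site, about 6.5 measurements per provider, provider ICC 0.35 (3.3.1), and participation of 99%, 75% and 49% by phase (5.5).
- Assumed: number of coders, tenure and severity spread. A severity SD of 0.1 to 0.3 outcome SDs is 0.1² = 1% to 0.3² = 9% of total variance.

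The model has a provider intercept, cluster indicators, PH_IMP and PH_SUS. There is no true TMI effect.

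**4. False-positive rate for PH_IMP, by time coding.**

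| Time coding | Coders only: four at a time, 4-6 cycle tenure, SD 0.1-0.3 | Coders and actors: 2-8 of each, 12- or 24-month tenure, 1-10% of variance each |
|---|---|---|
| Linear month | 6-12%; up to about 20% in other runs | 5.4-24% |
| Linear + quadratic month | 5-14% (SD 0.2-0.3 only) | about 5-12% (2-10% of variance) |
| Linear month + phase-specific slopes | 5-8%; up to 11% in another run | about 5-7% |
| Phase averages, no time term | 11-41% | 8-59% |
| Calendar-quarter indicators | about 5% | about 4-5% |
| Linear month, stable coders | about 5% | about 4-5% |

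The runs differ in their turnover and attendance assumptions. Attendance was either a flat 6.5 / 12 = 54% of 12 cycles or falling by phase.

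**5. One setting in full.** Four coders, 12-month tenure, linear month, coders only: 6.4%, 8.1% and 11% when coders carry 2%, 5% and 10% of variance. With four actors on the same footing: 7.9%, 11% and 20%. A check by fitted REML models (200 data sets per setting), with coders and actors at 5% each, gave 12%, against 5.5% with no rater variance. The Monte Carlo standard error near 12% is √(0.12 × 0.88 / 200) = 2.3 points.

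**6. After the change.** Coder indicators return the rate to about 5% (3-7% in one simulation). The PH_IMP standard error is 1-4% larger in one set of runs and 0-8% larger in another. With coder and actor both as random effects, the rate is 5.0%.

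**The case against.** The strongest reply is that the size is assumed. The documents do not say that any coder or actor left. The only turnover they mention concerns site facilitators: "The funding may be split among two facilitators to account for staff turnover". Coders were trained and monitored, and at a severity SD of 0.1 one run gave only 6.2-6.5% with a linear month term. With stable coders there is no inflation. All of this stands.

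A second reply is that this is largely a matter of time coding. SAP 5.2.3 also lists months since the start of implementation and of sustainment, and with those slopes most of the inflation goes. This stands in part. SAP 5.4.1 tests the level shift first and the slopes only if that is supported, so a linear month term is a fair reading. SAP 5.3 (item 5) also leaves phase averages open, which is the worst case when no time term is used.

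Stronger readings are tempting and are not supported:
- A reader might infer that the plan has a false-positive rate of 9-20%. That range belongs to one set of assumptions about turnover, severity and time coding.
- A reader might infer that each score averages several coders. It averages 12 items; the number of coders per recording is not stated. The list of rater types in SAP 2.3.1 describes the scale generally, so it does not show that supervisors scored trial recordings.
- A reader might infer that actor differences are equally established. Their number is not given, and actor effects enter the figures only by assumption.

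**Conclusion.** The gap is documented: an unadjusted item mean, more than one coder, no coder term, and no planned step that could add one. The mechanism follows from the staggered design. Its size cannot be read from the documents; it depends on coder turnover, severity spread and a time coding that the SAP has not fixed. With coder turnover assumed as in the first column of the table, the false-positive rate for PH_IMP runs from about 5% to 12% when the model includes a linear month term, with or without phase slopes, and to about 20% in less favourable runs. It is far higher only if phase averages are used with no time term. If the coding group was stable, nothing is lost.

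This is worth settling before the final model is run, because Hypothesis 1 rests on this contrast and the remedy costs little. It is not evidence that an observed TMI effect would be spurious.

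**What to change.** In SAP 5.2.3 and 5.4.1, add coder ID to the primary model: fixed indicators if there are few coders, otherwise a crossed random effect. Add standardised-patient actor ID as well if it was recorded. State how many coders and actors served, over which cycles, and how recordings were allocated to them.

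If coder IDs are not available, replace the linear month term with calendar-quarter indicators. This is second best: it absorbs changes shared by all sites in a quarter, but not a coder tied to particular sites. Its effect on the standard error should be reported, since the figures above do not give it.

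Keep the unadjusted raw-average model as a sensitivity analysis. Use a many-facet Rasch score only if double-coded recordings exist to link the coders; the documents describe reliability monitoring and practice coding but no such set.

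The cost is SAP wording, a merge of IDs, and a PH_IMP standard error a few percent larger (up to about 8%) when a time term is in the model. Reliability monitoring suggests that coder IDs exist; it says nothing about actor IDs.
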